### **7.3 Statistical Inference (Estimation)**

To meet the primary objective, this study will estimate the proportion of major congenital malformations in the erenumab-aooe exposed cohort and compare to the proportion of major congenital malformations in the unexposed internal comparator using the risk ratio and 95% CI.

## 8. Research Question and Objectives

### 8.1 Primary

The primary objective is to estimate the proportion of major congenital malformations in infants of women with migraine exposed to erenumab-aooe during pregnancy compared to infants of women with migraine unexposed to erenumab-aooe (internal comparator).

### 8.2 Secondary

Secondary objectives include the following:

- In women exposed to erenumab-aooe during pregnancy,
  - To estimate the proportion of pregnancy complications
  - To estimate the proportion of spontaneous abortion, still birth, elective termination, and preterm birth
- In infants of women exposed to erenumab-aooe during pregnancy,
  - To estimate the proportion of small-for-gestational age
  - To estimate the proportion of minor congenital malformations
  - To estimate the proportion of postnatal growth and development deficiency through the first year of life
- To compare the proportion of maternal, fetal, and infant outcomes of women with migraine exposed to erenumab-aooe consisting of women with migraine who have not been exposed to erenumab-aooe before or during pregnancy (internal comparator)
- To compare the frequency of major congenital malformations of women with migraine exposed to erenumab-aooe during pregnancy with women representing the prevalence of birth defects in the general population (external comparator)

## 9. Research Methods

### 9.1 Study Design

The design of this pregnancy exposure registry is consistent with relevant guidelines and recommendations ([FDA, 2019](#); [European Medicines Agency, 2005](#); [Gliklich et al, 2014](#); [Andrews et al, 2008](#)). This prospective observational registry will collect primary data from pregnant women with migraine and their healthcare providers (HCPs) (eg, primary care physician [PCP], neurologist [indication specialist], obstetrician [OB], nurse midwife or pediatrician) from the U.S. (see [Study Design Schema](#)). The coordinating center (CC) is responsible for obtaining informed consent and all patient and HCP contacts during the study. Patients' data obtained via questionnaires administered to patients or their HCPs will be recorded on electronic case report forms (eCRFs) by the CC.

Women who have been exposed to erenumab-aooe during the 16 weeks prior to their last menstrual period (LMP) or at any time during pregnancy are eligible for the

erenumab-aooe-exposed study cohort. The 16-week exposure period prior to LMP accounts for the effective half-life of erenumab-aooe (28 days; AIMOVIG® Prescribing Information), with an additional buffer added. Inclusion of exposures prior to LMP is based on the half-life and standard of care dosing schedule of erenumab-aooe. Dosing and treatment duration of erenumab-aooe as part of this observational study is at the discretion of the HCP in accordance with local clinical practice and local labeling.

The internal comparator cohort (erenumab-aooe-unexposed) will consist of currently pregnant women with clinically confirmed migraine who were not exposed to any CGRP mAb during 5 half-lives prior to their LMP or at any time during pregnancy. Internal comparator cohort patients will be enrolled and follow the same study procedures for follow-up and data collection as the erenumab-aooe exposed cohort.

Major congenital malformations are the primary outcomes of interest for this study, and other pregnancy, maternal, fetal, and infant outcomes are classified as secondary. Data on risk factors, migraine treatment exposures, other therapeutic or environmental exposures, and adverse maternal, fetal, and infant outcomes will be collected from patients and their HCPs during pregnancy and through 1 year after birth (infant's HCP and/or the patient). Major and minor congenital malformations will be classified according to the Metropolitan Atlanta Congenital Defects Program (MACDP) classification system and evaluated by a committee of at least 3 qualified, independent teratologists using all available medical records.

The frequencies of outcomes will be presented in comparison to both existing databases and the internal comparator cohort. The primary analysis will be adequately powered to detect an a priori clinically meaningful difference in the proportion of major congenital malformations between the erenumab-aooe exposed cohort and the internal unexposed cohort.

The study is voluntary and exposure to erenumab-aooe or any other migraine treatment(s) during the study period will be according to national labeling and local standard of care. Any currently pregnant woman with migraine qualifying for either the exposed or comparator cohort, as defined above, will be eligible for the study unless they are participating in another investigational device or investigational drug study, currently taking an investigational medicinal product, or having taken an investigational product within 3 months prior to LMP or during pregnancy. Follow-up will cease if the patient is lost to follow-up, consent is withdrawn, death (mother and/or infant), study termination, or the study ends (whichever comes first). The total duration of per patient

participation is up to 21 months and the total expected duration of the study is approximately 7 years.

An interim analysis at 3 years will be performed to evaluate enrollment and to estimate sample size. Methods to increase registry awareness and enhance patient recruitment and retention are outlined in protocol [Section 9.4.4](#).

## **9.2 Setting and Study Population**

Patients or HCPs can initiate enrollment through the CC. HCPs (eg, PCPs, neurologists [indication specialists], OBs, nurse midwives) who treat patients with migraine including Investigators involved in ongoing or future clinical studies of erenumab-aooe will be informed of the study and asked to refer any patient who becomes pregnant to the study CC. Patients can express interest in enrolling in the Pregnancy Registry by providing contact details on the study website. The CC will contact any potential patients to review consent and initiate enrollment. Future studies involving erenumab-aooe sponsored by Amgen may provide protocol language that describes this Pregnancy Registry study and the process of referring any women who become pregnant. Reporting of pregnancy exposures to erenumab-aooe is voluntary. Awareness will be raised to HCPs that any potentially eligible pregnant patients (either for the exposed or the internal comparator cohort) should be referred to the registry as early as possible; ideally before prenatal testing has been performed. Pregnancies with known outcomes (ie, pregnancy loss or live birth) at the time of the initial report will not be included in the study but will be followed by Amgen according to standard post-marketing pharmacovigilance.

### **9.2.1 Study Population**

Currently pregnant women with clinically confirmed migraine in the U.S. who have been exposed to erenumab-aooe during the 3 months prior to their LMP or at any time during pregnancy will be considered for inclusion in the exposed study cohort. An internal comparator cohort will consist of currently pregnant women with clinically confirmed migraine who have not been exposed to any CGRP mAb, while secondary data sources will be used to compare results to external comparator cohort(s) representing the prevalence of birth defects in the general population (see [Section 9.2.4 Patient Eligibility](#)).

Women will be enrolled prospectively and may be enrolled from the post marketing setting or other clinical or observational studies of erenumab-aooe, unless prohibited by exclusion criteria noted in [Section 9.2.4.2](#). To reduce bias that may occur if outcome information is known prior to enrollment, women should be enrolled in the study as soon

as their pregnancy is known, preferably prior to any informative prenatal testing (where the knowledge of the primary study outcome of the pregnancy would be known – either normal or abnormal), and preferably in the first trimester before 20 weeks gestation. Women who receive any first trimester prenatal screening after enrollment (post-enrollment) will be included in the primary analysis. Decision criteria with regards to prenatal testing before enrollment (pre-enrollment) will be applied to the study population for inclusion into the primary analysis and is outlined in [Section 9.7.1.2](#). [Table 2](#) are the pertinent descriptions.

**Table 2. Timing and Results of Prenatal Screening Tests: Key Descriptions**

Groups Determined by Test and Result	Inclusion in Analyses
Pre-enrollment prenatal screening: women who have already received prenatal testing where the result is known prior to enrollment	Variable based on subgroup
Subgroup 1: Women who have all normal findings	Included in primary analysis; included in sensitivity analysis of known test result(s) prior to enrollment
Subgroup 2: Women who have pregnancies with aneuploid disorders or genetic disorders that cause major congenital malformations	Excluded from primary and secondary analysis; analyzed as a separate group
Subgroup 3: Women who have pregnancies with results ( normal or abnormal) that are unrelated to aneuploid disorders or genetic disorders that cause major congenital malformations	Included in primary analysis; included in sensitivity analysis of known test result(s) prior to enrollment
Women who had no prenatal screening prior to enrollment in the registry	Included in primary analysis; exclude aneuploid or genetic disorders
Women who had prenatal screening after enrollment in the registry	Included in primary analysis; excluded in primary analysis women who have pregnancies with aneuploid disorders or genetic disorders that cause major congenital malformations

**9.2.1.1 External Comparator Cohorts**

External comparators can provide additional context for study results, and will be used to descriptively characterize study results, with MACDP reports serving as the primary external comparator; representing the estimated underlying prevalence of major structural or genetic birth defects in the general U.S. population. Only aggregate, population-level data or published reports would be used for comparison. Further details of external comparator cohort analysis are in [Section 9.7.2.5.2](#).

#### 9.2.1.1.1 Metropolitan Atlanta Congenital Defects Program (MACDP)

The MACDP, a population-based tracking system for birth defects, was established in 1967 as the first population-based system for the active collection of information about birth defects in the U.S. (MACDP, 2016). Currently, the MACDP tracking system captures approximately 35,000 births per year from 3 large metropolitan counties in the Atlanta area (5 counties were captured in earlier years). MACDP has monitored trends in birth defects rates and has served as a case registry for descriptive, risk factor, and prognostic studies of birth defects. Since 1998, MACDP surveillance has required that any signs or symptoms of a defect in the child be reported before their sixth birthday. In a 2007 report, the MACDP presented data on the prevalence and descriptive characteristics of birth defects, including 67 individual defects, in metropolitan Atlanta, Georgia, from 1968 to 2003 (Correa et al, 2007).

The frequency of birth defects is measured as prevalence at birth, expressed as the number of affected infants per 1,000 live births. Major structural or genetic birth defects affected approximately 3% of births in the U.S. (CDC, 2008). The prevalence estimates of stillbirth in 2006 and 2008 using MACDP data were 8.0 and 7.6 per 1000 live births plus stillbirths (95% CIs: 7.3, 8.7, and 6.9, 8.4), respectively (Duke and Gilboa, 2014).

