Similar descriptive analyses summarized above will be performed on the internal comparator cohort consisting of pregnant women with migraine who were not exposed to erenumab-aooe. If sufficient numbers are observed, a subgroup analysis will be performed by exposure to other migraine preventive treatments (other than erenumab-aooe).

Outcome frequencies will be described with both the internal comparator cohort and other available background prevalence from external comparator cohort(s). The primary analysis will be adequately powered to detect an a priori clinically meaningful difference in the proportion of major congenital malformations between the erenumab-aooe exposed cohort and the internal unexposed cohort. The comparison of the erenumab-aooe exposed cohort to the internal comparator cohort will be performed using the risk ratio and 95% CIs.

In addition, comparisons may be explored using odds ratios (ORs) adjusted to relevant covariates as applicable, if sufficient number of outcomes are available in the subgroups. Sensitivity analysis for spontaneous abortion as occurring before 22 weeks of gestation, for congenital malformations excluding women with exposure to known or potential teratogenic medications during pregnancy, and other potential sensitivity analyses of interest (if sufficient numbers allow) will be performed.

Existing data from external comparator cohort(s) will be used to compare the prevalence of selected adverse pregnancy events and of selected adverse fetal, neonatal, and infant events at birth and through at least the first year of life of infants in the registry (where available). The MACDP will be the primary external comparator cohort. Reports from The European Surveillance of Congenital Anomalies (EUROCAT) will also be used for supportive evidence and comparisons of outcome prevalence, in addition to other possible external databases as they become available. These comparisons will be based on examinations of point estimates and 95% CIs from each of the sources, and no inductive statistical inferences will be made.

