### 9.2.8 Study Follow-up

Women will be followed from enrollment through the end of their pregnancy and infants will be followed through 1 year after birth. Specific data to be collected during different periods during the follow-up are detailed below. Safety reporting will be ongoing throughout the duration of the study.

---

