#### **9.7.1.2 Primary Analysis**

The final primary analysis will be conducted once all data collection is complete, including up to 21 months of follow-up for enrolled patients. Annual reports for safety reporting requirements will be generated, with an interim analysis at 3 years.

The primary outcome for this study is the comparison between proportions of major congenital malformations in infants of women with migraine exposed to erenumab-aooe during pregnancy with the unexposed internal comparator. All other outcomes will be classified as secondary. Variables identified for the subgroup analysis will be evaluated as potential confounders in the primary comparative analysis of the risk ratio for major congenital malformations in the erenumab-aooe exposed and unexposed internal comparator.

Data analysis for major congenital malformations will be based on the first trimester exposure to erenumab-aooe. Adjudicated major congenital malformations reported up to 1 year of age by the mother or by an HCP will be included in the primary analysis. Women who have received any first trimester prenatal testing after enrollment, with either negative or positive test result will be included in the primary analysis, **except**:

- Women who have received first trimester prenatal screening, in which either aneuploid disorders or genetic disorders that cause major congenital malformations have been detected, because these disorders are unrelated to medication use
- Any prematurity-related disorders and transient conditions
- Women where the outcome is known, prior to enrollment in the registry, either positive or negative, for major congenital malformations that are unrelated to genetic or aneuploid disorders will be analyzed separately as a subgroup analysis.

In addition to the comparison to an unexposed internal comparator cohort, results will be descriptively compared to existing data sources or published reports representing the general population prevalence of birth defects in the general population (see [Section 9.2.1.1.1](#)). Additional external data sources for comparison will be considered as they become available during the study.

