#### **9.7.2.5.2 External Comparator Cohort Analysis**

Outcome prevalence for major congenital malformations in the erenumab-aooe exposed cohort will be compared with available external comparator cohort(s) representing the background prevalence of birth defects in the general U.S. population. The MACDP will be the main external comparator cohort ([MACDP, 2016](#); [NBDPN, 2010](#)). In the event any European data sources become available for descriptive comparison to this registry, the EUROCAT classification of congenital malformations would be implemented to ensure comparability.

The difference in prevalence of major congenital malformations in erenumab-aooe exposed cohort and the external comparator cohort will be compared similarly as to the internal comparator, with the estimate of risk ratio (95% CIs). Categorical distributions available in the MACDP report will be summarized using the same categories among erenumab-aooe exposed pregnancies ([CDC, 2008](#)). Indirect standardization methods will be applied for categorical distributions of maternal age, gestational age, and race/ethnicity. Indirect standardization involves calculation of the observed number of events (ie, major congenital malformations) and applying the maternal age, gestational age, and race ethnicity distributions from the reference population (ie, MACDP) to calculate the expected number of major congenital malformations. The ratio of the observed number of major congenital malformations to the expected number of major congenital malformations is referred to as the standardized prevalence ratio (SPR). Adjusted prevalence can be calculated by multiplying the SPR by the crude congenital malformation rate.

Published EUROCAT reports may be considered as an external comparator; the information would serve as a general non-U.S. population for comparison. Other possible comparisons with external datasets with adjustment methods (ie, direct or indirect adjustment with a standard population) for relevant available categorical

distributions (eg, maternal age, race/ethnicity, gestational age) as noted in [Section 9.9.2](#) will be explored at the time of final analysis. It is important to emphasize that any external comparator data source and women enrolled in this study are two distinctly different, thus “external adjustment methods” for inference comparisons are limited.

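### The external comparison sets malformations counted to age 1 against a MACDP rate that can include defects reported up to the sixth birthday; taken alone, this unadjusted mismatch pulls the external ratio down

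*Protocol*

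**What the plan says.** **Registry window.** Protocol 9.2.8 states that "infants will be followed through 1 year after birth", and the last infant contact in 9.4.2 is at 52 weeks. Protocol 9.7.1.2 sets the counting rule: "Adjudicated major congenital malformations reported up to 1 year of age by the mother or by an HCP will be included in the primary analysis".

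**Comparator window.** Protocol 9.2.1.1.1 describes MACDP: "Since 1998, MACDP surveillance has required that any signs or symptoms of a defect in the child be reported before their sixth birthday". Protocol 9.7.2.5.2 gives its role: "The MACDP will be the main external comparator cohort".

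**Planned comparison.** It is a secondary objective in Protocol 8.2: "To compare the frequency of major congenital malformations of women with migraine exposed to erenumab-aooe during pregnancy with women representing the prevalence of birth defects". Under 9.7.2.5.2 the prevalence difference "will be compared similarly as to the internal comparator, with the estimate of risk ratio (95% CIs"), and an observed-to-expected ratio, the SPR, is added. On adjustment the same section says: "Indirect standardization methods will be applied for categorical distributions of maternal age, gestational age, and race/ethnicity".

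**Status.** The Abstract says of the external comparisons that "no inductive statistical inferences will be made", and 9.2.1.1 calls their use descriptive.

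**The concern.** A defect first recognised between the first and sixth birthdays can enter the MACDP rate but can never enter the registry numerator. None of the three standardization variables concerns how long a child is observed, so the planned adjustment leaves the gap untouched. The limitations text in 9.7.2.5.2 and 9.9.2 warns in general terms that the populations differ, without naming the window or its direction. Section 9.7.2.6.3, on sensitivity analysis for residual confounding and bias, is marked not applicable.

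What is at stake is how the external ratio is read. In a safety registry, a ratio near or below 1 invites reassurance, and part of that reassurance could come from shorter observation. The external figure may also carry more weight than intended: Section 6 anticipates low participation, and 9.9.3 says low enrollment could weaken the internal comparison and make covariate adjustment infeasible.

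**Working it through.** **Inputs from the protocol**
- Registry window: 1 year (9.2.8, 9.7.1.2).
- MACDP window: before the sixth birthday, since 1998 (9.2.1.1.1).
- Reference prevalence: 3% (9.2.1.1.1).
- Exposed live births: 749 (9.5, Table 4).

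**Input not in the protocol**
- f, the share of cases in the MACDP figure first identified after age 1. I assume 5%, 10% and 20%.

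**The plan's own figure.** The formula for two proportions (3% versus 6%, two-sided 0.05, 80% power, pooled variance, no continuity correction) gives 749 per group. The protocol does not state sidedness; two-sided reproduces its figure. Enrollment is 749 / (0.85 × 0.62) = 749 / 0.527 = 1421. Both agree with 9.5. The external comparison has no sample-size figure of its own.

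**Effect of the mismatch alone.** Suppose the two sources agree in everything except the window, and the drug effect is the same on early- and late-recognised defects. MACDP prevalence to age 1 is then 3% × (1 - f), and

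expected external ratio = true RR × (1 - f).

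The true RR that would appear as exactly 1.0 is 1 / (1 - f). The reference count is 749 × 0.03 = 22.47; matched to age 1 it is 22.47 × (1 - f).

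| Assumed f | Ratio if true RR = 1.0 | If 1.5 | If 2.0 | True RR shown as 1.0 | Window-matched expected count |
|---|---|---|---|---|---|
| 0 | 1.00 | 1.50 | 2.00 | 1.00 | 22.5 |
| 5% | 0.95 | 1.43 | 1.90 | 1.05 | 21.3 |
| 10% | 0.90 | 1.35 | 1.80 | 1.11 | 20.2 |
| 20% | 0.80 | 1.20 | 1.60 | 1.25 | 18.0 |

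**Effect on the confidence interval.** Treat the expected count of 22.47 as fixed and all 749 live births as contributing. The exact Poisson lower 95% limit then exceeds 1 only with at least 33 observed cases. The chance of that, with mean 22.47 × RR × (1 - f), is:

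| Assumed f | True RR 1.5 | True RR 2.0 |
|---|---|---|
| 0 | 57.1% | 97.3% |
| 5% | 45.5% | 94.5% |
| 10% | 33.8% | 89.7% |
| 20% | 14.4% | 71.1% |

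**Scale against sampling error.** With 22 observed cases the ratio is 22 / 22.47 = 0.98, exact 95% CI 0.61 to 1.48. Multiplying the expected count by (1 - f) moves the point estimate to 22 / 21.35 = 1.03, 22 / 20.22 = 1.09 or 22 / 17.98 = 1.22.

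**The case against.** **The comparison is secondary and descriptive.** The Abstract and 9.2.1.1 say so, 9.7.2.5.2 itself cautions that external adjustment supports little inference, and no decision rule or power claim rests on the ratio. This stands and limits the weight of the point. It does not remove it, because 9.7.2.5.2 still commits to a risk ratio, a confidence interval and an SPR that readers will interpret.

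**The size is unknown and could be negligible.** This stands. A sixth-birthday limit is only an upper bound on inclusion and does not show that many major defects surface after age 1. The rule dates from 1998, whereas the report cited for the 3% covers 1978-2005 (Section 14), so the rule applies to only part of that period. A shift of 5% to 10% is also small beside the interval of 0.61 to 1.48.

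**A reader might infer that the external comparison as a whole is biased toward no excess.** The documents do not support that. Several features can push the ratio up:
- Total prevalence in 9.7.2.4 counts cases in terminations and fetal deaths, while 9.2.1.1.1 expresses MACDP frequency per live births.
- Registry infants have scheduled contacts at 12, 26 and 52 weeks.
- Some studies cited in 7.2 report more malformations with migraine itself.

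In the other direction, the registry excludes aneuploid and certain genetic disorders (Table 2, 9.7.2.1), while the MACDP figure covers structural or genetic defects. The net direction is open.

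**A reader might also infer that one year of follow-up cannot support the objective.** That goes too far: a descriptive comparison remains usable if the reference rate is matched or the mismatch is stated with a range.

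**The choice of reference tabulation could be left to the SAP.** In part. However, 9.7.2.5.2 already fixes the estimator and the standardization variables, and it neither matches the window nor defers that question.

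**Conclusion.** The point holds for this one mismatch. Both windows are stated in the protocol and nothing aligns them. Taken alone, the difference multiplies the external risk ratio and SPR by (1 - f), which cannot exceed 1. With assumed f of 5%, 10% or 20%, the null ratio is 0.95, 0.90 or 0.80. These values rest on an assumed f and on the two sources being otherwise comparable, so they show sensitivity and do not estimate the bias. The net bias of the external comparison is not established. The primary internal risk ratio is not touched, because 9.1 applies the same follow-up procedures to both cohorts and 9.7.1.2 the same 1-year limit. The change is worth making because it alters what an external ratio at or below 1 can be taken to show.

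**What to change.** 1. In 9.7.2.5.2, specify MACDP rates limited to defects identified by the first birthday wherever a published or aggregate tabulation allows it. Whether one exists cannot be told from the protocol, which relies on aggregate data or published reports.
2. If none is available, report the unrestricted risk ratio and SPR together with a sensitivity range that multiplies the expected count by (1 - f) over a pre-specified range of f.
3. State in 9.7.2.5.2 and 9.9.2 that the unequal window pulls the ratio down, so a ratio at or below 1 is not by itself evidence of no increase.
4. A list of defect groups recognisable by 1 year, drawn up by the blinded teratology committee, may be a supplementary analysis only. It should not replace the main external comparison: it would drop observed registry cases, and MACDP cases within a listed group could still have been diagnosed later.

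The cost is wording and one short sensitivity table, with no extra follow-up. The downside is a slightly lower reference prevalence, or a wider reported range, for a secondary descriptive comparison.
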